## **Statistical Analyses**

Sample size estimates for pilot studies are inherently difficult because by intent, a pilot study is meant to include a smaller sample than a fully powered study. The enrollment sample of 15 participants in the intervention group and 15 participants in the placebo group (allowing for at least 12 evaluable participants in each group after the expected 20% loss due to attrition) is intended to provide sufficient data to indicate feasibility of a larger study and to provide descriptive estimates of effects. Additionally, it will provide for nominal estimation (using a 95% confidence interval) of the mean changes in the inflammatory marker, IL-6, the primary outcome of this pilot.

Feasibility and acceptability of the proposed intervention in older adults will be evaluated by process variables including number of participants completing the study; medication compliance, number and severity of adverse events, and changes in Quality of Life attributable to study participation.

Efficacy will be assessed as effects of the intervention on functional performance (physical and cognitive measures; pain perception, and inflammatory processes (Specific Aims). The following outcomes will be evaluated: physical function (walking speed, muscle fatigue); cognitive function (attention, executive, and memory function); pain (self-report); and systemic inflammation (IL-6, CRP, TNF $\alpha$ , and novel markers)

For each outcome, we will take the value of that outcome after the 3-month supplementation period minus the value at baseline for each participant. Summary statistics and 95% confidence intervals will be provided for within group changes as well as between group differences.

Effect size of intervention on key outcomes for sample size calculations in the planning of a larger RCT. Based on a sample size of 15 per group and 20% attrition, we have 80% power to detect a between group difference of effect size 1.2. Specifically, if we use the root mean squared error from LIFE-P (adjusted for baseline log(IL-6) and treatment) of 0.52 for log(IL-6), then we can detect a mean difference of 0.62 (on the log scale) or equivalently the difference between 4.20 and 2.26 pg/ml (or a 46% difference). And for selection based on walking speed change, we used a within group standard deviation of 0.25, which leads to a detectable mean difference of 0.3 m/s.

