### **Enrollment and Randomization**

24 eligible participants will be enrolled and randomized to allow for 6 participant failures or withdrawals

At the baseline visit, the Informed Consent document for the RCT will be reviewed with the potential participant and written consent obtained. Participants will undergo a battery of physical performance tests (400-meter walk; short physical performance battery, grip strength and endurance), formal tests of cognitive function, and a blood draw of about 60 ml (See Table 1). Quality of Life and pain will be assessed with the AM-PAC, the SF-36, and the Brief Pain Inventory (BPI). Self-report of physical activity and dietary fat intake will be obtained through brief questionnaires (RAPA and Block High Fat screen).

Participants will then be randomized to receive either curcumin (1000 mg/day; n = 15) or placebo (microcrystalline cellulose; n=15) for a three-month period. The study drug will be provided for the first month according to randomization.

Participants in both groups will be instructed to return to the research center every month for the duration of the three-month trial. At the monthly visits, compliance with the supplementation regimen for the previous month will be assessed by pill count and participants will be provided with another month's supply of study medication according to initial randomization. Participants will be queried about any adverse events they experienced since their previous visit and any medical history updates they may need to provide. Additionally, blood samples will be obtained (chemistry 15 panel and complete blood count) to ensure that no adverse changes have occurred since their previous visit.

To enhance retention and to ensure participant safety, participants will receive bi-weekly telephone calls throughout the intervention period to ascertain adverse events and express appreciation for participation.

Following the three month supplementation period (Month 3 visit), participants will complete a post-treatment assessment including the battery of physical performance tests (400-meter walk, short physical performance battery, grip strength and endurance); cognitive function tests; questionnaires for quality of life, pain symptoms, and physical activity; and a blood draw of approximately 60 ml (See Table 2).

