e. Pain Assessments. The Brief Pain Inventory (BPI) will be used to assess the presence and location of daily pains, as well as pain severity and pain-related interference. The BPI measures pain severity using a series of 0 (no pain) to 10 (worst possible pain) scales, which assess average pain, worst pain, and least pain in the past week, as well as current pain at the time of testing. There are seven BPI interference questions, each ranging from 0 (does not interfere) to 10 (completely interferes), assessing the extent to which pain has interfered over the past 24 hours with general activity, mood, walking ability, normal work, relations with other people, sleep, and enjoyment of life. This instrument has been validated for assessing outcomes in participants with non-cancer pain and has been used to quantify treatment outcomes.

f. Systemic Inflammatory biomarkers. Standard inflammatory biomarkers (i.e., IL-6, TNFa, and novel markers of inflammation) will be measured by ELISA at Baseline and the 3-month visit. All samples will be measured in duplicate and the average of the two measures will be used for data analyses.

g. Other measures

Dietary Fat (Block) questionnaire. Poor absorption of curcumin has been reported for various preparations, with enhanced absorption in high fat diets. This brief (13 item) "fat screen" identifies individuals with "high" fat intake, a potential confounder due to enhanced curcumin absorption.

Self-reported physical activity. The Rapid Assessment of Physical Activity (RAPA) is a 9-item questionnaire developed to assess strength, flexibility, and level and intensity of physical activity among older adults.

Safety. As a safety check to ensure no adverse biological changes have occurred, the following measures will be completed at screening, baseline, and each monthly visit:

- Study Coordinator will review any changes in medication, ED visits or hospitalizations, or side effects since previous visit with the participant
- At monthly visits, 30 cc of blood will be drawn and analyzed for a CHEM-15 metabolic profile (Albumin, Albumin/Globulin Ratio (calculated), Alkaline Phosphatase, ALT, AST,

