BUN/Creatinine Ratio (calculated), Calcium, Carbon Dioxide, Chloride, Creatinine with GFR Estimated, Globulin (calculated), Glucose, Potassium, Sodium, Total Bilirubin, Total Protein, Urea Nitrogen) as well as for a complete blood count (WBC, RBC, Hemoglobin, Hematocrit, MCV, MCH, MCHC, RDW, Platelet Count, MPV and Differential (Absolute and Percent - Neutrophils, Lymphocytes, Monocytes, Eosinophils, and Basophils).

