Specific information on side effects observed in clinical trials is limited due to the small size of most studies, the patient populations (ages and diseases studied), different doses and composition of curcumin, and the efficacy focus of the clinical research. The most commonly reported side effects include upset stomach, nausea, dizziness, and diarrhea. In a recently published multi-center clinical trial comparing ibuprofen to curcumin extract in the treatment of osteoarthritis, curcumin extract was associated with fewer adverse events than ibuprofen in all complaints except loose stools, although differences were statistically significant only for abdominal pain/distension (see Table 3 below).

Table 3. Adverse Events	Ibuprofen 1200 mg (n = 182)	Curcumin extract 1500 mg/day (n = 187)	P-value
--------------------------------	-----------------------------------	--	---------

	Mean age 60.9 yr	Mean age 60.3 yr	
Number of patients with AE	65 (35.7%)	55 (29.7%)	0.222
Number of events	33 (18.1)	20 (10.8)	0.046*
Abdominal pain and/or distension	29 (15.9%)	21 (11.1%)	0.201
Dyspepsia	15 (8.2%)	9 (4.9%)	0.091
Nausea	16 (8.8%)	22 (11.9%)	0.324
Loose stools	2 (1.1%)	-	0.245
Melena	13 (7.1%)	7 (3.8%)	
Pitting edema			
Kuptmiratsakul V et al. Efficacy and safety of Curcuma domestica extracts compared with ibuprofen in patients with knee osteoarthritis: a multicenter study. Clinical Interventions in Aging 2014;9 451-458 (Reference 74)			

Monitoring for Adverse Events (AEs). An Adverse Event (AE) is any unfavorable and unintended sign (including an abnormal laboratory finding), symptom, or disease temporally associated with a study intervention that *may* or *may not* be related to the intervention. At monthly study visits, participants will be queried about specific AEs as above and instructed to report any additional adverse effects they experience related to the study coordinator or other member of the investigative team. Basic blood chemistry and CBC from each visit will be reviewed by the Safety Monitor (study physician).

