Grading scales found in the National Cancer Institute (NCI) Common Terminology Criteria for Adverse Events (CTCAE) version 4.0 ([http://evs.nci.nih.gov/ftp1/CTCAE/CTCAE\\_4.03\\_2010-06-14\\_QuickReference\\_8.5x11.pdf](http://evs.nci.nih.gov/ftp1/CTCAE/CTCAE_4.03_2010-06-14_QuickReference_8.5x11.pdf)) will be utilized for AE reporting. All AEs will be reviewed by the Safety Monitor (study physician) upon ascertainment.

- Grade 1 adverse events are mild; asymptomatic or mild symptoms; clinical or diagnostic observations only; intervention not indicated
- Grade 2 adverse events are moderate; minimal, local, or noninvasive intervention indicated; limit age-appropriate instrumental ADLs (preparing meals, shopping for groceries or clothes, using the telephone, managing money, etc.)
- Grade 3 adverse events are severe or medically significant but not immediately life threatening; hospitalization or prolongation of hospitalization indicated disabling or limit self-care ADLs (bathing, dressing and undressing, feeding self, using the toilet, taking medications, and not bedridden)
- Grade 4 adverse events have life-threatening consequences, urgent intervention indicated
- Grade 5 adverse event are fatal, resulting in death.

Common Terminology Criteria for Adverse Events (CTCAE) (Version 4.0) are defined for gastrointestinal side effects reported with curcumin in Appendix A.

Study medication will be stopped for the following reasons:

- Moderate to severe adverse effect symptoms limiting participant continuation in the study (Grade 3 or 4 toxicity)
- Elevation in liver function tests to 2x upper limits of normal or increase in serum creatinine to 1.5x baseline value
- Decrease in hemoglobin of > 1 g/dL from previous visit
- Development of medical problems listed as exclusion criteria
- Need for medications listed as exclusion criteria

As curcumin is well-tolerated, no Grade 3 or 4 toxicities are expected and no dose modifications are planned for this study.

This study will have a Safety Monitor (study physician) for continuous monitoring of individual participant results, and aggregate data will be reviewed semiannually by the Claude D. Pepper OAIC DSMB (see above).

2. Risks associated with blood draw. Risks include discomfort with the puncture and the possibility of a small bruise at the puncture site. To avoid these risks, research staff are trained in proper phlebotomy techniques

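### The only planned adverse-event summary is an event count with no breakdown by arm, no rule for repeat reports and no separation of laboratory findings from symptoms; a by-arm, participant-level table should replace it

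*Combined protocol and SAP*

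**What the plan says.** The Statistical Analyses section judges feasibility and acceptability by process variables. These include the number of participants who complete and "medication compliance, number and severity of adverse events, and changes in Quality of Life attributable to study participation". Completion is counted in participants; AEs are counted in events. The 95% intervals in that section, within and between groups, are specified for outcomes expressed as the month-3 value minus the baseline value.

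Section 7 (Monitoring for Adverse Events) defines an AE as "any unfavorable and unintended sign (including an abnormal laboratory finding), symptom, or disease temporally associated with a study intervention", whether or not it is related to the intervention. The grading list that follows says "Grade 1 adverse events are mild; asymptomatic or mild symptoms; clinical or diagnostic observations only; intervention not indicated". On expected effects, section 7 states: "The most commonly reported side effects include upset stomach, nausea, dizziness, and diarrhea". Appendix A gives grades for gastrointestinal terms.

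On collection, section 7 says "At monthly study visits, participants will be queried about specific AEs as above", and Enrollment and Randomization adds that "participants will receive bi-weekly telephone calls throughout the intervention period to ascertain adverse events". Under Outcome Measures (Other measures, Safety), "At monthly visits, 30 cc of blood will be drawn and analyzed for a CHEM-15 metabolic profile", "as well as for a complete blood count (WBC, RBC, Hemoglobin, Hematocrit, MCV, MCH, MCHC, RDW, Platelet Count, MPV and Differential". The study physician reviews laboratory results and AEs.

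**The concern.** The first stated objective is to show that the intervention is feasible and acceptable, and a larger trial would be planned on that evidence. For tolerability, the useful quantity is how many people in each arm had a problem, of what kind and how bad. The plan collects what is needed for this (specific AE queries, gastrointestinal grades, monthly laboratory tests), but no planned summary uses it that way.

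A single count of events has three weaknesses here. It is not assigned to arms. It can grow when one person mentions the same symptom at successive contacts. It can also place an asymptomatic laboratory value and a mild gut symptom in the same Grade 1 cell, so tabulating by severity does not separate them.

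**Working it through.** 1. **The plan's own figures.** The plan gives none for AEs. Its only power statement does reproduce: 15 × 0.8 = 12 per group, and a two-sample t-test with standardised difference 1.2 and two-sided alpha 0.05 (assumed; not stated) has 80.2% power, against the stated 80%. That figure concerns efficacy outcomes and does not bear on this point.

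2. **Is a by-arm AE estimate planned?** The intervals apply to month 3 minus baseline. AEs accumulate during follow-up and have no baseline value, so they fall outside that rule. The sentence on process variables names no comparison.

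3. **Repeat reporting.** Table 2 marks AE queries at the 1-, 2- and 3-month visits and at Weeks 6, 10 and 15-16, which is 6 contacts. The bi-weekly calls imply a Week 2 call as well, making 7. One participant with one persistent symptom can therefore yield from 1 to 7 entries, depending on an unwritten logging rule. A count of participants gives 1 in every case.

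4. **Laboratory entries.** Values per draw: 17 chemistry + 10 blood count + 5 cell types × 2 (absolute and percent) = 37. Dropping the 3 calculated chemistry items and the 5 percentages leaves 29. The text specifies 3 monthly draws. Expected flags = values × draws × rate. The rate is not in the documents; 1% to 5% is assumed, with every flag logged as an AE.

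| Values per draw | Per participant, 1% to 5% | Per 12 participants | Per 15 participants |
|---|---|---|---|
| 37 | 1.11 to 5.55 | 13.3 to 66.6 | 16.7 to 83.3 |
| 29 | 0.87 to 4.35 | 10.4 to 52.2 | 13.1 to 65.3 |

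   If staff log only values they consider important, the number could be near zero.

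5. **Effect on a total, events against events.** This simulation is illustrative: 12 per arm, a gut event in 30% versus 10% of participants, each counted once, and laboratory flags with the same mean in both arms but varying between people. All of these inputs are assumed, and the totals are split by arm, which the plan does not do. At 0, 1.11 and 5.55 flags per participant, the median ratio of total counts is 2.33, 1.16 and 1.03. The arm with the higher gut-event rate has the strictly higher total in 85%, 59% and 52% of runs. This shows how dilution would work; it does not predict that it will happen.

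6. **Comparability with the plan's own evidence.** Table 3 in section 7 reports participants with any AE: 29.7% on curcumin extract. Applied to a curcumin arm only, that is 0.297 × 12 = 3.6 or 0.297 × 15 = 4.5 participants. An event count cannot be compared with this. (The printed 55 of 187 is 29.4%, an immaterial difference. Lower rows of that table appear misaligned in the text as read and are not used.)

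7. **Precision of the replacement.** With 0 of n affected, the exact upper 95% limit is 1 − 0.025^(1/n): 21.8% for n = 15 and 26.5% for n = 12. With 2 of 15, the exact interval is 1.7% to 40.5%.

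**The case against.** The case against is substantial on size.

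- The plan says number and severity, so grades will be available. This stands, except within Grade 1, where mild symptoms and asymptomatic findings meet.
- The AE item is one process variable among several, with no threshold attached. Completion and pill-count compliance are also measured, and gut intolerance strong enough to reduce adherence would partly show there. This stands and limits what is at stake.
- The laboratory arithmetic needs two assumptions: the flag rate, and the logging of every flag as a new AE. The definition requires a finding to be unfavourable and temporally associated, and a physician reviews results. This stands. The review does not, however, amount to a written recording rule.
- Laboratory changes are not mere noise. Section 7 discusses glucose, iron absorption and bleeding, and its reasons for stopping include laboratory criteria. This stands, and is why laboratory AEs need their own by-arm table and should not be removed.
- At this sample size a participant-level table is imprecise too. True, but its intervals show that imprecision, whereas a bare count hides it.

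A reader might infer that laboratory values and repeat reports will swamp the gut side effects, or that harm will appear in the wrong arm. The documents support neither. They give no flag or logging rates, and a count that is not split by arm cannot favour one. Setting expected laboratory events beside the number of participants with an AE would also mix units.

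**Conclusion.** The concern holds in a limited form. As written, the plan yields no participant-level, by-arm estimate of tolerability, and its event count can mix Grade 1 laboratory findings with mild symptoms and can count a continuing symptom more than once. The count could mislead about how well curcumin is tolerated. The extent is unknown: the 13 to 67 laboratory entries per 12 participants rest wholly on the assumed 1% to 5% flag rate and full logging, and the 1-to-7 range for a persistent symptom rests on how staff record repeat reports. The primary outcome, IL-6, is unaffected. This is a worthwhile, inexpensive improvement to the analysis text and does not threaten the trial's main result.

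**What to change.** Change the tabulation only. The AE definition, collection, safety review and stopping rules stay as they are, and no laboratory finding is added to or removed from the AEs. In Statistical Analyses, replace the AE item with text such as:

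*For each arm, we will report the number and proportion of randomised participants with at least one AE, with at least one symptomatic AE (any AE not recorded solely from a laboratory result), and with each gastrointestinal term in Appendix A and dizziness, each participant counted once per row at worst grade. Exact 95% confidence intervals will be given for each arm, with a 95% interval for the difference between arms. Laboratory AEs will be shown in a separate table by arm. A continuing symptom counts once per participant. Event counts will be given as a secondary listing.*

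Name the method for the difference interval in advance.

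The denominator must be reconciled first. Enrollment and Randomization gives 24 randomised and also 15 + 15, and Statistical Analyses uses 15 + 15.

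The cost is a few sentences and two small tables from data already collected. The downside is the wide intervals shown under the working, which should be printed and not used to claim that curcumin is well tolerated.

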### Study Population

The RCT will include 24 moderately functioning, sedentary adults age 70 years or older with elevated levels of systemic inflammation but without overt disease conditions. We estimate that up to 324 potential participants will undergo screening procedures to identify 24 persons eligible for enrollment in the RCT.

Based on our previous studies, we anticipate that the average age of participants will be approximately 77.0 years, and that approximately 20% will be African Americans. In general, participants will have a relative low prevalence of comorbid diseases.

The key inclusion criteria are the following:

- (1) Age  $\geq 70$  years;
- (2) Mild to moderate physical impairment (Short Physical Performance Battery score  $\leq 10$ );
- (3) Sedentary lifestyle ( $< 120$  min per week of moderate intensity physical activity);
- (4) Chronic low-grade inflammation measured by IL-6  $> 2.5$  pg/ml. To minimize within person variability, IL-6 is the average of 2 measures taken 1-3 weeks apart at screening visits

See Table 1 for a complete list of eligibility criteria.

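### The detectable IL-6 difference of 0.62 log units (46%) assumes baseline adjustment on the log scale, but the only stated analysis is month 3 minus baseline with no scale or covariate

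*Combined protocol and SAP*

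**What the plan says.** The Statistical Analyses section makes IL-6 the primary outcome and promises "nominal estimation (using a 95% confidence interval) of the mean changes in the inflammatory marker, IL-6, the primary outcome of this pilot". The rule for building every outcome is: "For each outcome, we will take the value of that outcome after the 3-month supplementation period minus the value at baseline for each participant". The planned output is then: "Summary statistics and 95% confidence intervals will be provided for within group changes as well as between group differences". No transformation, covariate or model is named there, and no other section supplies one.

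The log scale and the baseline adjustment appear only in the power paragraph that closes the section. Starting from 15 per group and 20% attrition, it states that "we have 80% power to detect a between group difference of effect size 1.2". It converts this to IL-6 units with an SD borrowed from another study (described as the "root mean squared error from LIFE-P (adjusted for baseline log(IL-6) and treatment) of 0.52 for log(IL-6") and concludes that "we can detect a mean difference of 0.62 (on the log scale) or equivalently the difference between 4.20 and 2.26 pg/ml", which it also gives as 46%.

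Three places bear on which IL-6 value counts as baseline:

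- Outcome Measures, item f, says the inflammatory markers "will be measured by ELISA at Baseline and the 3-month visit".
- Table 2, as extracted, marks IL-6 at screening and at month 3 but not at the baseline visit.
- Study Population says, for eligibility, that "IL-6 is the average of 2 measures taken 1-3 weeks apart at screening visits".

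**The concern.** The 0.52 is what remains of the variation in log(IL-6) after baseline and treatment have been regressed out. The analysis rule describes a plain difference. Taken literally, it leaves at least three analyses open: a change in pg/mL, an unadjusted change in log(IL-6), and a log change adjusted for baseline. Only the last is sure to keep the SD behind 0.62. The plan is silent here rather than contradictory.

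The scale-free statement (80% power at 1.2 SD) is not in question. What is open is its translation into 0.62 log units and 46%. This matters because one of the overall objectives in the Specific Aims is an effect size for planning later trials. A standardised effect depends on its SD, and a mean change in pg/mL cannot be set directly against a planned 46% ratio. Two statisticians could both follow the rule and report different primary estimates.

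The choice of baseline sample also matters. If the value used for selection against the entry threshold serves as baseline, within-group changes are exposed to regression to the mean.

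**Working it through.** **Inputs.** From Statistical Analyses: 15 per arm, 20% attrition, hence 12 evaluable per arm; effect size 1.2; adjusted SD 0.52 for log(IL-6); stated difference 0.62; 4.20 vs 2.26 pg/mL. Assumed: two-sided alpha 0.05 (none is stated for the power calculation) and a two-sample t-test.

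**Step 1: reproduce the plan.** 15 × 0.8 = 12. With 12 per arm and d = 1.2, power is 80.2%; the exact detectable d at 80% is 1.197. Then 1.2 × 0.52 = 0.624, given as 0.62. 1 − exp(−0.62) = 46%, and 4.20 × exp(−0.62) = 2.26. The figures are right for a baseline-adjusted analysis of log(IL-6).

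**Step 2: SD of an unadjusted log change.** Write month-3 log(IL-6) = a + b × baseline + e, with SD(e) = 0.52 and baseline log-SD s. The change is a + (b − 1) × baseline + e, so

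SD(change) = √(0.52² + (1 − b)² s²).

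This equals 0.52 only when b = 1. The documents give neither b nor s. If baseline and month-3 variances are equal, b = rho, s = 0.52/√(1 − rho²), and SD(change) = 0.52 × √(2/(1 + rho)).

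**Step 3: put numbers in (12 per arm).** Detectable difference = 1.197 × SD; effect size of 0.62 = 0.62/SD.

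| rho | implied s | SD(change) | detectable difference | from 4.20 pg/mL to | power for 0.62 | effect size of 0.62 |
|---|---|---|---|---|---|---|
| 0.3 | 0.545 | 0.645 | 0.77 (54%) | 1.94 | 61% | 0.96 |
| 0.5 | 0.600 | 0.600 | 0.72 (51%) | 2.05 | 68% | 1.03 |
| 0.9 | 1.193 | 0.534 | 0.64 (47%) | 2.22 | 78% | 1.16 |
| baseline-adjusted SD | – | 0.52 | 0.62 (46%) | 2.26 | 80% | 1.19 |

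The rho 0.9 row needs a baseline log-SD of 1.19, which is extreme. The 95% CI half-widths are 0.546, 0.508 and 0.452 for the three change-score rows, against 0.441 for the covariate model. Unequal variances move the result either way: at rho 0.7, a month-3 to baseline SD ratio of 0.8 gives 0.79 log units and a ratio of 1.25 gives 0.63.

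**Step 4: allow for the entry threshold.** Simulation, 20,000 trials per setting: log-normal IL-6, median 4.20 before truncation, baseline truncated at 2.5 pg/mL, residual SD 0.52, effect −0.62, no placebo drift, slopes 0.3 to 1.0. Power by baseline log-SD before truncation (after truncation 0.34 / 0.46 / 0.58):

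| analysis | 0.4 | 0.6 | 0.8 |
|---|---|---|---|
| unadjusted log change | 72–80% | 66–80% | 59–80% |
| change in pg/mL | 57–69% | 44–62% | 33–57% |
| log scale, baseline as covariate | 77–78% | 77–78% | 77–78% |

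At slopes of 0.8 or more, the unadjusted log change keeps 78–80%. The truncation is approximate because entry uses the mean of two screening values. The 2.5 threshold is that of Study Population and Table 1; the Design section gives 2.0, which needs separate reconciliation. The low ends of the pg/mL row depend on the no-drift assumption; a variant simulation gave 56%, 39% and 24%.

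**The case against.** The strongest reply is that this is a descriptive pilot. Its sample is justified by feasibility and estimation, no hypothesis test is named, and the 0.62 is openly conditional on an SD whose adjustment is disclosed. Month 3 minus baseline does not rule out logging or adjusting, and the adjusted analysis can still be run on the same data. All of that stands. It limits the consequence, but it does not supply the missing scale and model.

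A second reply is that the alternative sizes are fragile, which is also fair. If the implied baseline SDs in Step 3 are read as values before truncation at 2.5 pg/mL, the detectable differences shrink to 0.72, 0.68 and 0.63 (51%, 49% and 47%) and power for 0.62 rises to 68%, 72% and 79%. All three differences still exceed 0.62. The pg/mL results rest on assumed log-normality, median and SD, and should carry little weight beyond their direction.

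Third, different standardisers are not an error, since a later planner can use the difference together with its SD. That works only if the report says which scale and which SD it used.

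Fourth, item f of Outcome Measures does say the markers are measured at Baseline, and Table 2 came through extraction with a damaged header. The table is therefore weak evidence of conflict. The baseline sample should still be named, because the eligibility value is a different one.

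**Conclusion.** The concern holds as a gap in specification, not as an arithmetic or validity error. The 80% power at 1.2 SD is correct. Its conversion to 0.62 log units and 46% is assured only for a log-scale analysis adjusted for baseline, which the plan does not state.

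For an unadjusted log change under equal variances, the detectable difference is 0.64 to 0.77 log units (47% to 54%) for rho 0.9 to 0.3, with power for 0.62 of 78% to 61%. If the slope on baseline is 0.8 or more, the loss is immaterial. For a change in pg/mL the 46% has no direct counterpart, and power was lowest in every range simulated. All sizes rest on an assumed correlation, baseline SD and alpha; the silence on scale and covariate rests on none of these.

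Everything above uses 12 evaluable per arm. Design, Study Population and the opening of Enrollment and Randomization give 24 enrolled in total, against 15 per arm later in that section and in Statistical Analyses. With 9 or 10 evaluable per arm, power at 1.2 SD is 67% or 72% on any scale. That conflict is a separate matter to reconcile.

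**What to change.** Add to Statistical Analyses, for IL-6: month-3 log(IL-6) will be analysed by a linear model with treatment and baseline log(IL-6); the adjusted geometric mean ratio with its 95% CI and the residual SD will be reported; raw and within-group changes are descriptive. This matches the SD already used for planning and gives later trials an effect with a defined SD.

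Name the pre-treatment IL-6 value that serves as baseline (the baseline-visit sample or the screening values) and align Table 2 with it.

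If unadjusted change scores are kept, state the scale and restate the 0.62 (46%) for a declared correlation and variance assumption. Under equal variances on the log scale without truncation, that is 0.77, 0.72 or 0.64 at rho 0.3, 0.5 or 0.9.

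The cost is wording for one outcome and one model degree of freedom: at 12 per arm and equal SD, a CI half-width of 0.441 instead of 0.440 log units. No new data or visits are needed. The choice should be fixed before unblinding. The other outcomes and the walking-speed figure are not questioned here.
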